6.0	25 Feb 2021	
 • Removed details related to focus groups proposed under aim 1. It was decided that individual interviews were more appropriate to obtain the necessary data. Focus groups were therefore removed from the protocol. • Removing focus groups required increasing individual interviews with patients in order to reach saturation. The number of individual interviews were estimated to be 15-20; these have been increased to 24. Participant totals changed to reflect this change. • Data collection was modified to reflect that the AIM 2 patient baseline survey will be administered either in person or by telephone; and the patient eligibility screener may be collected on paper or REDCap. We are remaining flexible to accommodate different characteristics of the study sites and staffing. • We changed the location of the study to Hanoi only. This change is due to COVID restrictions which limit travel within the country and reduction in budget. • The definition of standard care for the intervention was changed from 3As (Ask, Advise, Assist)+ referral to 2As (Ask, Advise) + referral. The text and figures were edited to reflect this change. This change was made in response to results of the formative data that demonstrated that physicians did not have time to provide more intensive assistance (the 3rd A) • Recruitment and enrollment information was edited to account for changes based on the formative research findings. • The Quitline referral process was changed in order to increase the likelihood that patients will receive counseling. Patients will now be called by the Quitline rather than having to initiate the call. • Data protection around Quitline referral process was added. • The medical clearance form that listed the conditions that require precautions when prescribing NRT was removed; questions were moved to the screening for eligibility form, which is completed by a nurse at each clinic. We have deleted uncontrolled hypertension and unstable angina based the current recommendations on risks of NRT. • The number of weeks that NRT will be provided was changed from 4 to 6 weeks. This was because the cost of gum is less than the patch which allows us to now provide the NRT for the recommended minimum number of weeks of treatment. • We are adding a pilot study in Aim 1

		
 • We are adding a text message protocol to enhance the counseling intervention. Patients randomized to arm 2 and 3 of the RCT will receive 2 messages per day for 8 weeks and then one per day until end of treatment which is 12 months.
7.0	October 19	
 • A set of cost questions was added to the patients baseline survey • Added a fourth aim that will study the relationship between food insecurity and tobacco use among people living with HIV/AIDS in Vietnam. This aim was added as part of a supplement that the team received. • Increased the sample size by 75 from 672 to 747 to include 75 non-smokers as part of Aim 4. • Added details about Aim 4 to the recruitment, enrollment, consent, and statistical considerations sections. • Revised OPC eligibility: patient minimum per site was changed from 250 to 240. A minimum number of providers per site was added, 4 providers per site to ensure that we had enough sites to enroll. • CO measure was changed from >8ppm to >10ppm which is consistent with the literature • Revised the protocol for the three arms to go back to the original 3As (Ask, Advise, Assist) vs 2As. This was based on findings from the formative assessment. Revised the workflow to reflect the RA obtains consent from the patient rather than the clinic nurse and that the RAs will be onsite to complete all consent and baseline survey forms.
8.0	December 29 2022	
 • Added bullet point added to patient eligibility inclusion criteria to address any potential double enrollment from any patient who participated in the intervention during wave 1 so they are not enrolled during wave 2. • Removed 12-month patient follow up survey, the 6-month patient follow up survey provides sufficient information on intervention completion.
9.0	August 16 2023	
 • Updated all mentions of conducting sustainability assessment at 12 months to conducting it at 18 months because we needed additional time after study completion to adequately assess sustainability.

Table of Contents

Statement of Compliance	6
List of Abbreviations.....	6
Protocol Summary	7
Schematic of Study Design.....	8
1. Key Roles.....	9
2. Background and Scientific Rationale.....	9
2.1 BACKGROUND.....	9
2.2 DESCRIPTION OF MEDICATION	9
2.2.1 Dose and Rationale	9
2.3 RATIONALE.....	10
2.4 POTENTIAL RISKS AND ENDPOINTS	10
2.4.1 Potential Risks	10

HIV	Human Immunodeficiency Virus
ISMS	Institute of Social and Medical Studies
KI	Key informant interviews
MI	Myocardial infarction
NIDA	National Institute on Drug Abuse
NIH	National Institutes of Health
NRT	Nicotine replacement therapy
NYU	New York University
OPC	Outpatient clinic
OTC	Over the counter
PHI	Protected health information
PI	Principal investigator
PLWH	People living with HIV
QC	Quality control
RA	Research assistant
RCT	Randomized controlled trial
SAC	Scientific Advisory Committee
SAE	Serious adverse event
SAP	Statistical and analytic plans
SC	Standard care
SoM	School of Medicine
TUT	Tobacco use Treatment
UP	Unreported problem
VHW	Village health worker
WHO	World Health Organization

PROTOCOL SUMMARY

Title	Implementation of tobacco use treatment in HIV clinics in Vietnam
Brief Summary	The primary objective of this study is to conduct a 3-arm randomized controlled trial (RCT) that compares the effectiveness of three multi-component interventions that are embedded in HIV outpatient clinics (OPCs): 1)3As+Referral (Standard Care (SC)): Ask about tobacco use, Advise to quit, Assist with brief counseling and Refer to Viet Nam's national Quitline; 2) AAA+ +Counsel (Counsel=6-session cessation counseling intervention adapted for patients living with HIV/AIDS (PLWH) and delivered by a trained, onsite nurse; and 3) AAA+Counsel+N (N=nicotine replacement therapy (NRT)). The main outcome is biochemically validated 6-months smoking abstinence. We will recruit and randomize 672 patients across 13 outpatient clinics (OPCs) (48 per site, 16 per arm). We will also recruit 75-nonsmokers to participate in a single survey to assess food safety. Therefore, the total sample = 747 patients.
Phase	Phase 3
Objectives	
The primary objective of this study is to conduct a 3-arm RCT that compares the effectiveness of three multi-component interventions to increase smoking abstinence among PLWH.
 
The secondary objective is to assess factors (health care setting, provider, and patient level factors) that may influence tobacco cessation, and sustainability of the interventions tested.
 
The primary objective of the supplement is to examine the difference in household food insecurity among people living with HIV and the relationship between food insecurity and tobacco use in Vietnam.

Methodology	The is a 3-arm unblinded RCT
Endpoint	The primary endpoint is carbon monoxide confirmed smoking abstinence at 6 months.
Study Duration	Five years
Participant Duration	Patients and providers will be enrolled for 2 years
Duration of IP administration	Nicotine gum (for those randomized to Arm 3 in the RCT) will be given for 6 weeks.
Population	We are recruiting tobacco users who are patients at one of the 13 participating OPCs. All patients are Vietnamese. We will recruit women and men. For the research supplement (AIM 4) we will recruit non-smokers from the 13 OPCs.
Study Sites	13 HIV outpatient clinics in Hanoi
Number of participants	941 (includes providers and patient participants)
Description of Study Agent/Procedure	The intervention being tested in the RCT is behavioral only in ARM 1 and 2 and in ARM 3 patients will also receive nicotine gum for daily use for 6 weeks.
Reference Therapy	NA. There is no placebo. This is an effectiveness study using an over the counter drug.
Key Procedures	NA

Statistical Analysis	The primary analytic approach used to compare study arms is conditional logistic regression. This fixed effects approach was chosen as primary because of the modest number of sites and the fact that they are not very heterogeneous. Because some methodologists have advocated mixed effects models even when the number of sites is small, we will use a multilevel logistic regression model as an alternative, sensitivity analysis approach. In an intent-to-treat analysis of all study entrants, conditional logistic regression analysis will compare study arms on the primary outcome, 7-day point prevalence CO confirmed (<10 ppm) tobacco abstinence captured at 6-month follow up. The outcome will be regressed on indicator variables for study arm and OPC site will be the stratification variable. Pairwise comparisons of arms will be undertaken to determine which arms are significantly different. Pairwise comparisons will be adjusted for multiple comparisons using the Tukey method. Effect magnitudes will be based on odds ratios for the pairwise comparisons, which will be calculated by exponentiating the coefficients for pairwise contrasts. Secondary cessation outcomes, HIV-related outcomes, hypothesized mediators (e.g., risk perceptions, self-efficacy), and the food insecurity outcomes also will be analyzed with conditional logistic regression, or a different fixed effects regression appropriate to the type of outcome variable.
----------------------	---

SCHEMATIC OF DESIGN. This research has three phases. For Aim 1 we will conduct a formative

assessment to inform further modifications to the intervention components. Participants in Aim 1 will be patients of the outpatient clinics (OPC) or health care providers who work there. Patients who use tobacco will be asked to participate in individual interviews (n=24). We will conduct key informant interviews with health care providers from 3 OPCs (n=28) to adapt the intervention to the OPC clinical context. We will then conduct a pilot test of ARM 1 and 3 in one OPC with 16 patients. The recruitment and enrollment process will be the same as described for Aim 2. For Aim 2 we will conduct a three-arm randomized controlled trial (RCT) to compare the effectiveness of three interventions aimed at increasing tobacco cessation rates among people living with HIV/AIDS (PLWH). Patients (n=672) will be recruited and enrolled from the 13 OPCs. All enrolled patients will complete a baseline survey in person. This survey will be administered once eligibility is established and consent is obtained. The consent and survey will last 30 minutes. Follow up surveys will occur at 3- and 6-months after enrollment. Follow up surveys will be conducted by telephone. At 6-months follow up, patients who report smoking abstinence will be asked to come in person to the OPC and will complete a carbon monoxide test to validate self-report. We will conduct baseline and 12-month surveys with all health care providers in the study sites in person (n=98). For Aim 3 we will conduct 12-month post intervention interviews and an 18-month survey to assess factors associated with implementation effectiveness and potential for sustainability. For Aim 4 we will enroll 75 more patients who are non-smokers for a total of (n=747) patients and assess the relationship between food insecurity and tobacco use among PLWH (75 smokers and 75 non-smokers), which includes administering the Household Food Insecurity Access Scale (HFIAS) survey to patients at baseline and 6-months.

2.2 DESCRIPTION OF MEDICATION

2.2.1 Dose and rationale. We will be using nicotine gum which is an FDA approved medication for smoking cessation. This medication is over the counter and therefore poses minimal risk. We will be providing gum of 2 mg for 6 weeks which is consistent with trials of efficacy.^{2,3} Despite the burden of disease related to tobacco use, there is a lack of evidence for the long-term effectiveness of tobacco cessation interventions for PLWH. Inadequate implementation of evidence-based tobacco use treatment interventions in HIV treatment settings exacerbates the health and economic burden caused by the high prevalence of smoking in Viet Nam. Developing and implementing effective tobacco cessation interventions is critical for optimizing treatment outcomes and survival for PLWH who use tobacco.

2.3 POTENTIAL RISKS AND BENEFITS

2.3.1 Potential risks. This study poses minimal risk to both patients and employees enrolled in the study. Loss of confidentiality is the greatest potential risk to study subjects. All participants will receive an identification number that will be used for all forms, transcripts, surveys and intervention materials. For patients, we are using two behavioral interventions and nicotine gum. The nurse conducting enrollment will assess risk factors related to the use of nicotine replacement therapy (NRT) that would exclude patients from enrolling. Patients with a recent history of myocardial infarction (MI) (two weeks), serious underlying arrhythmias, and patients who are pregnant or nursing will not be offered NRT. It is important to note that the nicotine gum is an over-the-counter medication, with proven safety, and with minimal potential side effects. In addition, there are no significant interactions between NRT and HIV treatments (<http://www.hivdruginteractions.org/PrintableCharts.aspx>). Recent changes in FDA labeling also confirm that it is safe for tobacco users to use NRT while continuing to smoke. The FDA label for over the counter (OTC) NRT now says that: “concomitant use of OTC NRT products with cigarettes or with other nicotine-containing products does not raise significant safety concerns”. Employees in the participating health clinics will be asked to sign consent which will explain the voluntary nature of their participation and that they can withdraw their participation at any time without consequences in terms of risk to employment. Employee data will be treated as described above to ensure that their responses to survey questions and interviews remains confidential and cannot be linked to any employment records. The enrollment and consent procedures to ensure that there is no coercion are described below in section 12.1.

2.3.2 Potential benefits. Patients who receive the counseling and/or nicotine gum may quit using tobacco.

3. OBJECTIVES. The objectives of the main study are 1) to conduct a formative assessment to guide adaptations of the current intervention components to optimize implementation of tobacco dependence treatment, 2) to conduct a 3-arm randomized controlled trial (RCT) that compares the effectiveness of three multi-component interventions that are embedded in HIV OPCs, and 3) to assess barriers and facilitators to implementation and potential for sustaining gains. (See schematic above). The objectives of the supplement are 1) to estimate the difference in household food insecurity among PLWH who smoke compared with PLWH who are non-smokers at baseline. 2) to examine mechanisms linking smoking and household food insecurity among PLWH at baseline and 6-months follow-up, and 3) to assess the impact of a reduction in tobacco use and tobacco cessation on measures of food Insecurity at 6-month follow-up.

4. STUDY DESIGN and ENDPOINTS

4.1 DESCRIPTION OF STUDY DESIGN. This is a phase 3 pragmatic comparative effectiveness study. **AIM 1:** We will collect pretrial data using individual interviews with tobacco users to inform further tailoring of the intervention for HIV+ smokers and individual interviews (n=28) with health care providers in three OPCs. We will then conduct a pilot test of ARM 1 and 3 in one OPC with 16 patients. **AIM 2:** We will then conduct a 3-arm RCT to compare the effectiveness of three multi component interventions: 1) Ask, Advise, Assist (AAA) + Refer to the national smokers' Quitline); 2) AAA+Counseling (Counsel) which adds referral to an onsite health worker for 6-sessions of cessation counseling tailored to PLWH; and 3) Addition of 6-weeks of nicotine gum (AAA+Counsel+N). Only ARM 3 participants will receive NRT. ARM 2 and 3 will receive two text messages daily for 8 weeks and then 1 per day for 4 weeks to reinforce the counseling protocol. A total of 747 participants will be recruited in 13 outpatient HIV clinics (OPCs) in Hanoi and randomized into one of the three arms (48 smokers per site, 16 per arm; about 5 non-smokers per site). The primary outcome for smokers is 6-months biochemically validated smoking abstinence. We will conduct baseline in person surveys with all providers (n=98).

AIM 3: We will conduct 12-month post intervention interviews and 18-month surveys with healthcare providers and other key informants to assess factors associated with implementation effectiveness and potential for sustainability.

AIM 4: We will collect data on food insecurity from 75 non-smokers and 672 smokers at baseline and 6-months.

4.2 STUDY ENDPOINTS
4.2.1 Primary. The primary endpoint is carbon monoxide confirmed smoking abstinence at 6 months.

4.2.2 Secondary. The secondary patient outcomes are self reported smoking cessation and reduction in number of cigarettes per day, and hypothesized mediators of the main outcome (risk perception, attitudes, norms and self-efficacy) at 3 and 6 months.

5. STUDY ENROLLMENT AND WITHDRAWAL.

5.1 INCLUSION CRITERIA.

5.1.2. Study site eligibility. We will recruit 13 OPCs from one city, Hanoi. The sites are very homogeneous in terms of staffing and infrastructure. Therefore, site eligibility will be based solely on the number of active patients to ensure adequate recruitment (>240 patients) and at least 4 providers per site. The CDC of Hanoi will assist with site recruitment.

5.1.3. Patient inclusion criteria. For Aim 1-3 men and women who are ≥ 18 , patients in the HIV OPCs, current tobacco users, live in Hanoi and reachable by phone are eligible. All patients of the OPCs are HIV+. We expect fewer women to be enrolled in all phases of this research because about 10-20% of patients in the OPCs are female, and their smoking prevalence is low (<2%). There are no enrollment restrictions based upon race and ethnicity. For the supplement we will enroll men and women who are >18 and patients in the HIV OPCs who are not current tobacco users.

5.1.4. Health care providers and staff inclusion criteria. All providers and staff currently working at the OPC will be eligible.

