5.4.3. AIM 3. At the time of enrollment in AIM 2, providers will also be asked to participate in the KIs 12 months after the intervention period. Consent will be obtained at the time they enroll in AIM 2. For the 18-month sustainability survey, written consent will be obtained at the time they are approached to participate in the survey.

5.4.4. Aim 4. We will enroll 75 patients who are non-smokers using the same strategy as AIM 2.

5.5 DURATION OF STUDY PARTICIPATION. Patient individual interview participants will be asked to participate for the single session. Providers and patients who participate in the RCT will be enrolled for 2 years. Patients who are non-smokers (n=75) participating in the diversity supplement study will be enrolled for six months.

5.6 TOTAL NUMBER OF PARTICIPANTS AND SITES. For Aim 1, we will conduct 24 patient interviews and 28 provider interviews across 3 OPCs. We will recruit 16 patients in the one OPC that will serve as the pilot study site. For Aim 2 we include 672 patients (48 patients per site, 16 per arm). Surveys will be conducted, at baseline, with all health care providers in the 13 sites in person (n=98). For Aim 3, we will repeat surveys and KIs among the 48 providers with 2 health care providers per site, 13 sites, (n=28) at 12-months post intervention, and will separately conduct a sustainability survey at 18-months with the same providers. For Aim 4, we will include 75 patients (at least 5 patients per site).

5.7 PARTICIPANT WITHDRAWALS OR TERMINATION.

5.7.1. Reason for withdrawal. This is a minimal risk study so we do not expect participants to withdraw for a safety-related issue. However, participants (providers and patients) are free to

withdraw from participation in the study at any time upon request without any impact on their ability to continue to receive care or to be employed.

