Healthcare provider recruitment: Health care workers will be told about the study at a group meeting. It will be made clear to them that participation is voluntarily and they don't have to participate. This will be repeated at the time of the consent process. All health workers are eligible. Research staff will follow-up to contact providers and staff to make appointments for to administer the baseline and follow up surveys. Written consent will be obtained at the time of the baseline survey. Health care providers who participate in surveys will be asked to complete the survey again at 12 months post intervention. We are requiring that the interviews are audiotaped, as described above. We will let potential participants know about the audio taping at the time we describe the study to offer them an opportunity to decline at that time if that is a reason they do not want to participate. However, we will again explain that the interviews will be audio taped prior to beginning at which time they will have another chance to opt out.

AIM 3: Provider interviews. Health care workers who were enrolled in AIM 2 will have been consented to also participate in interviews and surveys post intervention to assess the implementation process.

AIM 4: Patient recruitment: non-smokers will be recruited using the methods described for recruiting smokers as detailed in AIM 2 patient recruitment above.

7.1.2 Enrollment/Baseline.

AIM 1: Patient Interviews: We will confirm eligibility and then ask participants to choose an interview date. Participants will be offered an explanation of the purpose of the study, given a one-page description with a number to call if they have additional questions. We will obtain verbal consent at the time of the interview immediately before it begins.

AIM 1 and 3: Provider surveys and KIs: We will confirm eligibility which only includes that the provider is currently working at the OPC. Providers will be asked to provide verbal consent for preintervention interviews and written consent to enroll in the longitudinal assessment (surveys and KIs). The initial survey and KI will occur at baseline and then they both will be repeated at 12 months. A separate survey to assess sustainability will be conducted at 18 months, for which written consent will be obtained before administering the survey.

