7.1.3 Study visits

AIM 1 Patients: The first and final visit for patients in AIM 1 is the interview. Patients enrolled in the AIM 1 pilot study will complete the same study visits as described below in Aim 2.

AIM 1-3 Providers: Provider visits include in person KIs for Aim 1 (n=28). For Aim 2 providers will be asked to complete a baseline survey (n=98) and KIs (n=28) across the 13 study OPCs. For AIM 3 we will repeat the survey and KIs at 12 months, and separately conduct a sustainability survey at 18 months.

AIM 2 RCT and AIM 4: Patients will be asked to complete a baseline, 3-, and 6-month survey. The baseline survey will take place in person. All other surveys will be conducted by telephone, 3 and 6-months. At 6-months follow up patients who report smoking abstinence will be asked to come in person to the OPC and will complete a carbon monoxide test at the OPC to validate self-report.

7.1.4. Methods and Procedures.

AIM 1: Patient Interviews. Experienced interviewers from our partnering institution in Vietnam (i.e., Institute for Social and Medical Studies, ISMS) will conduct these interviews (n=24). The number of interviews will depend on reaching saturation.

AIM 1-3: Health care provider surveys and interviews. All interviews and surveys will be administered by experienced ISMS staff. The interviews will be digitally recorded, transcribed and translated and stored as described above. We will not conduct the interviews if participants refuse to have the interview recorded. Surveys are administered using REDCap on iPads at baseline and 12 months and 18 months post intervention.

AIM 2 RCT and AIM 4: All patient surveys are administered using REDCap. The baseline patient survey is conducted in person at the time of enrollment. All other surveys will be conducted by telephone, 3- and 6- months. At 6-months follow up patients who report smoking abstinence will be asked to come in person to the OPC and will complete a carbon monoxide test at the OPC to validate self-report. The CO test involves the patient blowing through a small cardboard tube into a small handheld monitor which measures the amount of CO expired. A positive test (i.e., still smoking) will be defined as >10ppm. The CO test visit will take about 20 minutes and the findings will be recorded in REDCap.

7.1.5. Withdrawal/Early termination visit. The clinical site, patients and providers may withdraw from the study at any time.

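### Section 5.1.3 requires smokers, but not the Aim 4 non-smokers, to live in Hanoi and be reachable by phone; this unequal entry rule could confound the baseline food-insecurity contrast and leaves the 6-month telephone survey unsecured.

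*Combined protocol and SAP*

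**What the plan says.** Section 5.1.3 sets two entry rules. For Aims 1-3, patients aged 18 or over who are "current tobacco users, live in Hanoi and reachable by phone are eligible". For the supplement: "For the supplement we will enroll men and women who are >18 and patients in the HIV OPCs who are not current tobacco users". The second rule has no residence condition and no phone condition, and its age cut is strictly above 18.

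The clinics are shared. Section 5.1.2 states "We will recruit 13 OPCs from one city, Hanoi", and the Protocol Summary adds "For the research supplement (AIM 4) we will recruit non-smokers from the 13 OPCs".

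Two sections link non-smoker recruitment to Aim 2. Section 5.4.4: "We will enroll 75 patients who are non-smokers using the same strategy as AIM 2". Section 7.1.1: "non-smokers will be recruited using the methods described for recruiting smokers as detailed in AIM 2 patient recruitment above".

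On follow-up, section 4.1 (Aim 4) says "We will collect data on food insecurity from 75 non-smokers and 672 smokers at baseline and 6-months". The Schematic of Design and section 5.5 also keep non-smokers to six months. Section 7.1.3 covers the Aim 2 trial and Aim 4 together: baseline is in person, then "All other surveys will be conducted by telephone, 3 and 6-months". The Protocol Summary disagrees and describes a one-off survey for the 75 non-smokers.

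**The concern.** Supplement objective 1 (section 3) is the baseline difference in household food insecurity between patients who smoke and patients who do not. That contrast is observational, so it depends on both groups entering under the same rules apart from smoking. As written, a clinic patient who lives outside Hanoi or has no phone is barred as a smoker and admitted as a non-smoker. Residence and phone access are plausible markers of household means, which may be related to HFIAS. Stratifying by clinic does not remove a residence difference within a clinic.

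The second issue is follow-up. Section 5.7.2 counts a participant as lost after four failed phone attempts and does not replace losses. Smokers are screened for phone access before facing the telephone survey; non-smokers are not.

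**Working it through.** **1. Do other sections supply the missing conditions?** Sections 5.4.4, 7.1.1 and 7.1.2 carry over the recruitment process: nurse check-in, screening, consent and baseline survey by the research assistant. They state no criteria. The Aim 2 criteria could not carry over unchanged in any case, because they require current tobacco use. Section 5.1.3 is therefore the only text that says who qualifies as a non-smoker.

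**2. The plan's own figure.** Section 9.1 (Aim 4) gives 80% power for d = 0.46 with 75 smokers and 75 non-smokers, SD 6. It states no alpha; two-sided 5% is assumed here. A two-sample comparison gives 79.9% (t) or 80.4% (normal), so the figure reproduces. The detectable difference is 0.46 × 6 = 2.76 points, which the plan rounds to 3.

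**3. Possible shift in the baseline contrast.** The shift equals the share of non-smokers whom the smoker rule would have excluded, times the difference between their mean HFIAS and that of the other non-smokers. Both inputs are assumptions.

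| Share | Gap 1 point | Gap 3 points | Gap 6 points |
|---|---|---|---|
| 5% | 0.05 | 0.15 | 0.3 |
| 10% | 0.1 | 0.3 | 0.6 |
| 20% | 0.2 | 0.6 | 1.2 |
| 30% | 0.3 | 0.9 | 1.8 |

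Against 2.76 points, the range is 0.05/2.76 = 2% to 1.8/2.76 = 65%. A middle case of 10% and 3 points gives 0.3/2.76 = 11%, or 0.3/6 = 0.05 SD.

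**4. Effect on the test.** The standard error is 6 × √(2/75) = 0.98. By normal approximation, with shift b:

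- With no true difference, the rejection probability is Φ(−1.96 + b/0.98) + Φ(−1.96 − b/0.98). It is 5.0% at b = 0.05, 6.1% at 0.3, 23% at 1.2 and 45% at 1.8.
- With a true 2.76-point difference and a shift against it, power is about Φ((2.76 − b)/0.98 − 1.96). It is 79% at b = 0.05, 71% at 0.3, 36% at 1.2 and 17% at 1.8.

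The lower part of the range is harmless and the upper part is not. The documents do not say where the trial lies.

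**5. Loss at 6 months.** Suppose 5%, 10%, 20% or 30% of the non-smokers were lost (again an assumption) and all 75 smokers stayed. The non-smoker group would be 71, 68, 60 or 52. Power for d = 0.46 in a two-group comparison would be 78.8%, 77.9%, 75.1% or 71.6%.

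This concerns objective 2 at 6 months only. The objective 1 contrast uses the in-person baseline survey, and the 6-month cessation analysis in section 9.1 uses smokers only. The shares in steps 3 and 5 are not the same quantity: a patient outside Hanoi who has a phone counts in step 3 but can still be surveyed.

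**The case against.** The best defence is that the supplement sentence is drafting shorthand. Section 7.1.2 gives Aim 2 and Aim 4 one joint procedure for screening, consent and baseline, so staff may have applied the same residence and phone questions to everyone. That is possible, but the text does not say so, and a screener following section 5.1.3 would not apply them.

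A different rule may also be deliberate. Smokers have counseling sessions and, if they report abstinence, an in-person carbon monoxide test; non-smokers have neither. The protocol does not give this reason, and it would not explain dropping the phone condition when the 6-month survey is by telephone.

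Several stronger readings are tempting and should be resisted:

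- A reader might infer two source populations. Both groups are patients of the same 13 Hanoi clinics, recruited by the same route; only an entry filter differs.
- A reader might infer that some non-smokers certainly cannot be reached. The documents give no share without a phone or living outside Hanoi, and either could be near zero.
- A reader might infer that the difference cannot be removed. Adjusting for residence by regression would be extrapolation, since no eligible smoker lives outside Hanoi. Restricting the comparison does remove it, if the items were recorded. Section 9.1 also plans an analysis of income against HFIAS, so part of the suspected mechanism is to be measured.
- A reader might infer that a true smoking effect could be reversed. Even the 1.8-point extreme is below the 2.76 points planned for, so an effect of that size could be masked but not reversed.

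The age wording (above 18 against 18 or over) affects only 18-year-olds and is not evidence of bias.

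**Conclusion.** The mismatch in the written criteria stands. Residence and phone access are required of one group in a two-group comparison and not of the other, and nothing elsewhere in the protocol supplies them. Whether this biases the baseline HFIAS contrast depends on two facts that the documents do not give: how many non-smokers live outside Hanoi or lack a phone, and how far their food security differs. Over the assumed ranges the shift runs from negligible to about two thirds of the detectable difference.

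The phone omission is a risk of loss for objective 2 at 6 months only, and only if non-smokers have a 6-month survey at all, on which the Protocol Summary disagrees with the other sections. This is a modest issue for a supplement objective. It does not affect the primary endpoint or any stated sample size or power, and it is worth correcting because the remedy is cheap.

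**What to change.** In section 5.1.3, rewrite the supplement sentence so that non-smokers meet the Aim 2 inclusion criteria other than tobacco use: the same age cut, patient of a participating clinic, living in Hanoi, reachable by phone. Record residence and phone access on the screener for both groups. In the same edit, reconcile the Protocol Summary (one survey) with the Schematic of Design and sections 4.1, 5.5 and 7.1.3 (follow-up to 6 months).

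If non-smokers have already been enrolled, restrict the smoker versus non-smoker comparison to those living in Hanoi and reachable by phone, where these items were recorded, and report how many are set aside. The price is precision: setting aside 5-30% of 75 leaves 71 to 52 non-smokers, and power for d = 0.46 falls from 79.9% to between 78.8% and 71.6%, by the arithmetic of step 5.

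Made before enrolment, the change costs one sentence and two screener items. A few non-smokers become ineligible, which should be manageable with about 75/13 = 5.8 needed per site. The planned 75 + 75 and its 80% power are unchanged.
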